2.2 Secondary objectives

The key secondary objective is to demonstrate in the patient pool of PASI 75 responders who do not reach a PASI 90 response at Week 24 that secukinumab 300 mg s.c. administered

every 2 weeks is superior to secukinumab 300 mg s.c. administered every 4 weeks at Week 52 based on the PASI 90 response rate.

Other secondary objectives are as follows:

- Evaluate the proportion of PASI 50, PASI 75, PASI 100 and IGA mod 2011 0/1 responder rates at Week 52.
- Evaluate the course of mean PASI over time from Week 24 to Week 52.
- Evaluate the effect of different maintenance treatment frequencies on PROs: Dermatology Life Quality Index (DLQI), EuroQOL 5-Dimension Health Questionnaire (EQ-5D[©]), Work Productivity and Activity Impairment Questionnaire-Psoriasis (WPAI-PSO), and the patient's assessment of pain, itching and scaling.

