9.4.4 Handling of missing values/censoring/discontinuations

Patients who drop out prematurely and/or do not have a valid PASI assessment at Week 52 will be counted as non-responders. Patients with major protocol violations, but with a valid PASI assessment will be included in the ITT-analysis with their observed response.

The same algorithm will be used for the key secondary endpoint, the PASI 90 response in the FAS-P75P set. Missing values for other endpoints will not be replaced.

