9.7 Sample size calculation

Based on the pooled data from the CAIN457A program (CAIN4572302 and CAIN4572303), the PASI 90 response rate for biologics-naïve patients treated with secukinumab 300 mg s.c. was 74.3% at 24 weeks. Of those who were PASI 90 responders at Week 24, 81.8% of patients maintained their PASI 90 response until Week 52.

It is assumed that a dosing frequency of 6 weeks (Group 2) will differ in PASI 90 response up to 7% worse compared a dosing frequency of 4 weeks (Group 1). This assumption of a difference of maximally 7% is based on simulation of the PK levels obtained with maintenance treatments of secukinumab 300 mg every 6 weeks and the correlation between plasma levels and the clinical response seen in the secukinumab Phase 3 studies.

A total of 554 patients per group are required to achieve 90% power on a one-sided, 2.5% significance level to demonstrate the non-inferiority of 6-weekly vs 4-weekly dosing, if the true maintenance rates are 81.8% under 4-weekly and 74.8% under 6-weekly dosing and the non-inferiority margin is predefined as -15%.

The response rates underlying this estimation were obtained from pooled data of studies analyzed according to the ITT-principle using the same algorithm to handle drop-outs or protocol violations as in this present study. Therefore, the effect of drop-outs or protocol violations should be already accounted for in the effect estimates and no further adjustments of the sample size are required. However, to account for the fact that there might be minor differences (eg with respect to drop-out rates) between the historical data and the data to be observed in this study, the sample size will be rounded up slightly to 570 patients/group who should be randomized to Group 1 or Group 2 (giving a total of 1140 patients in both groups) of this study.

Assuming a PASI 90 response rate of 74% at Week 24, 1580 patients should be enrolled at Baseline in this study in order to achieve the required sample size for randomization at Week 24. This number still allows for some drop-out patients or patients withdrawing consent at or after randomization even after experiencing a PASI 90 response.

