#### 1.8.3 Handling of missing values/discontinuations

Patients who drop out prematurely and/or do not have a valid PASI assessment at Week 52 will be counted as non-responders. Patients with major protocol violations, but with a valid PASI assessment will be included in the intention-to-treat (ITT)-analysis (i.e. primary analysis) with their observed response. The same algorithm will be used for the key secondary endpoint, the PASI 90 response at Week 52 in the FAS-P75R set. Missing values for secondary endpoints or other outcomes (e.g. quality of life, safety or lab measurements) will not be replaced.

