#### PASI score over time in Treatment Period 2 and Follow-Up Period

Summary statistics will be provided for absolute PASI scores as well as for absolute and percent change from baseline by visit and treatment group. The analysis will be performed until Week 52 in the FAS-P90R and until Week 60 for the FAS-P75R. Figures for mean course of the PASI score will also be provided.

The absolute PASI score will be analyzed by analysis of covariance (ANCOVA) models with dosing group, country and body weight stratum as explanatory variables and baseline value as covariate. ANCOVAs will be performed at each visit starting with Week 28.

## DLQI, EQ-5D, WPAI-PSO and assessment of pain, itching and scaling in Treatment Period 2

For the DLQI subscale and the DLQI total score, the EQ-5D VAS and the EQ-5D utility index, for each of the main outcomes of the WPAI-PSO and for the assessment of pain, itching and scaling, the absolute and percentage change from baseline to each visit during

Treatment Period 2 where the scales are assessed will be derived. Summary statistics will be provided for absolute values as well as for the percentage change by visit and dosing group.

Page 32

ANCOVA models with dosing group, country and body weight stratum as explanatory variables and baseline value as covariate will be performed for the visits Week 36, 48 and 52.

In addition, summary statistics will be provided for number of subjects achieving DLQI 0 or 1 at each visit where the DLQI is assessed. Risk differences including 95%-CIs will also be presented for the visits Week 36, 48 and 52.

For the single EQ-5D dimensions contingency tables will be provided for each visit where the scale was to be assessed. Changes from baseline to each visit will be displayed using the categories improved, unchanged and worsened in each dimension.

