#### 2.2.3 Multiple imputations for response variables

Non-responder imputation as primary analysis will be performed since low drop-out rates are expected. It is expected that subjects will be likely to drop-out due to lack of efficacy, such that a non-responder imputation will be reasonable.

In the multiple imputations analysis the response status will be imputed based on the individual treatment arm information.

Multiple imputation (MI) is a simulation based approach where missing values are replaced by multiple Bayesian draws from the conditional distribution of missing data given the observed data and covariates, creating multiple completed data sets. These completed data sets can then be analyzed using standard methods. Rubin (1987) presented rules how to combine the multiple sets of estimates to produce overall estimates and confidence intervals that adequately incorporate missing data uncertainty.

Missing values for the 'change from baseline PASI score' will be imputed based on an underlying joint normal distribution and using a Markov Chain Monte Carlo (MCMC) method. The change from baseline in PASI score appears to follow closer to a normal distribution than the actual PASI score.

Page 41

The imputations will be done separately for each dosing group including weight at Week 24 (in groups) as additional covariate. Values post assessment timepoint of the primary endpoint will not be considered for imputations.

The number of imputations will be set to 50, the seed for the random function will be set to 4573302 for this study. To generate the multiple imputed data sets, the SAS procedure MI can be used as follows:

The input data set <pasi> should have one record per subject with baseline PASI score as well as all changes from baseline PASI starting with Week 28.

```
ODS LISTING CLOSE;
ODS OUTPUT MissPattern=miinfo_msgpat VarianceInfo=varinfo ParameterEstimates=param;
PROC MI DATA=<pasi> OUT=<impdata> SEED=4573302 NIMPUTE=50;
 VAR <weight at Week 24> >
     <baseline PASI>
     <change from baseline PASI week 24> - <change from baseline PASI week primary endpoint>;
RUN;
ODS LISTING;
```

Two outputs will be prepared displaying i) the missing data patterns and the group means as stored in the data set msgpat and ii) the variance information and estimated means with confidence interval and range based on data sets varinfo and param which need to be merged by <dosing group>.

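### Mean PASI and the patient-reported outcomes are compared by visit-wise ANCOVA on observed cases; if drop-out follows the SAP's own expectation, the late-visit 6-weekly versus 4-weekly difference is probably somewhat understated

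*SAP*

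**What the plan says.** Protocol 2.2 makes mean PASI over time a secondary objective ("Evaluate the course of mean PASI over time from Week 24 to Week 52") and also lists the effect of dosing frequency on the DLQI, EQ-5D, WPAI-PSO and the pain, itching and scaling ratings.

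SAP 1.8.7 analyses absolute PASI with a separate model per visit: "ANCOVAs will be performed at each visit starting with Week 28". For the patient-reported outcomes, models with dosing group, country, body weight stratum and "baseline value as covariate will be performed for the visits Week 36, 48 and 52". SAP 2.1.2 repeats this model form and adds no longitudinal term.

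On missing data, SAP 1.8.3 states: "Missing values for secondary endpoints or other outcomes (e.g. quality of life, safety or lab measurements) will not be replaced". Protocol 9.4.4 agrees: "Missing values for other endpoints will not be replaced". Non-responder imputation covers only the primary and key secondary endpoints. The multiple imputation in SAP 2.2.3 is a sensitivity analysis for the primary endpoint (SAP 1.8.4).

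On drop-out, SAP 2.2.3 says "Non-responder imputation as primary analysis will be performed since low drop-out rates are expected", and adds: "It is expected that subjects will be likely to drop-out due to lack of efficacy". Neither document gives a rate, overall or by arm.

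**The concern.** With no replacement and one model per visit, the Week 52 comparison includes only patients still observed then. If patients leave because psoriasis returns, those missing at Week 52 are disproportionately those with high scores. At the planning rates in Protocol 9.7 (81.8% maintained on 4-weekly dosing, 74.8% on 6-weekly) there are more such patients in the 6-weekly arm. Removing them pulls the two observed means together.

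The secondary objective concerns the effect of dosing frequency in the randomised groups, not among those who did well enough to stay. In a non-inferiority trial, shrinkage towards no difference flatters the reduced regimen. In Groups 3 and 4 the same mechanism could hide part of a benefit of 2-weekly dosing.

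**Working it through.** **Plan's own figures.** No SD, effect size, power or drop-out rate is given for these ANCOVAs. The planning rates do reproduce the stated primary sample size: n = (1.960 + 1.282)² × (0.818×0.182 + 0.748×0.252) / (0.15 − 0.07)² = 10.507 × 0.3374 / 0.0064 ≈ 554 per group. The margin is (0.818/0.182)/(0.668/0.332) = 2.23. Both match.

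**What happens to an early leaver.** Protocol 5.5.10 and footnote c of Table 6-1 require the end-of-Treatment-Period-2 (EOT2) assessments, at least 4 weeks after the last dose. The patient is then registered as completing early. SAP 1.4.4 assigns values by study day. With a last dose at Week 36 and EOT2 at Week 40 (Day 281), the PASI value counts at Week 40 (Days 268–295) and not at Weeks 44, 48 or 52. SAP 1.4.3 labels the last visit as end of Treatment Period 2 but does not say that it enters the Week 52 ANCOVA.

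**Two-class calculation.** Let p be the share losing response (0.182 on 4-weekly, 0.252 on 6-weekly). Let q be the assumed probability that a response loser leaves before Week 52, and r the same for the others. The observed share of losers is

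s = p(1−q) / [p(1−q) + (1−p)(1−r)].

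If each class has the same mean score in both arms and leaving is random within class, the difference in means equals the difference in s times a constant. The observed difference in s divided by 0.070 is then the bias factor on the mean difference (1.00 = no bias).

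For q = 20%, r = 0: 4-weekly 0.1456/0.9636 = 0.151; 6-weekly 0.2016/0.9496 = 0.212; difference 0.0612; factor 0.0612/0.070 = 0.87.

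| q, 4-wk / 6-wk | r, 4-wk / 6-wk | Drop-out, 4-wk / 6-wk | Difference | Factor |
|---|---|---|---|---|
| 5% / 5% | 5% / 5% | 5.0% / 5.0% | 0.0700 | 1.00 |
| 10% / 10% | 0 / 0 | 1.8% / 2.5% | 0.0658 | 0.94 |
| 20% / 20% | 0 / 0 | 3.6% / 5.0% | 0.0612 | 0.87 |
| 20% / 20% | 5% / 5% | 7.7% / 8.8% | 0.0632 | 0.90 |
| 30% / 30% | 0 / 0 | 5.5% / 7.6% | 0.0561 | 0.80 |
| 50% / 50% | 0 / 0 | 9.1% / 12.6% | 0.0441 | 0.63 |
| 10% / 10% | 2% / 6% | 3.5% / 7.0% | 0.0742 | 1.06 |
| 10% / 30% | 3% / 3% | 4.3% / 9.8% | 0.0245 | 0.35 |
| 30% / 10% | 3% / 3% | 7.9% / 4.8% | 0.0998 | 1.43 |

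The 81.8% and 74.8% rates already count drop-outs as non-responders, so using them as true loss rates is an approximation.

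**Simulation.** Assumed inputs: 570 per arm, seven post-randomisation visits, 300 replicates, and leaving driven by the last observed PASI (above 2 points). The observed-case Week 52 difference is compared with a likelihood estimate using all visits, equivalent to an MMRM under monotone drop-out. Neither has covariates.

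| Hazard per visit if PASI > 2, 4-wk / 6-wk | Drop-out | True | Observed-case (factor) | Likelihood (factor) |
|---|---|---|---|---|
| 1% / 1% | 2.7% / 2.9% | 0.316 | 0.311 (0.98) | 0.316 (1.00) |
| 3% / 3% | 5.0% / 5.8% | 0.308 | 0.289 (0.94) | 0.307 (1.00) |
| 6% / 6% | 8.5% / 10.0% | 0.321 | 0.284 (0.89) | 0.321 (1.00) |
| 3% / 8% | 5.2% / 12.2% | 0.318 | 0.172 (0.54) | 0.315 (0.99) |
| 8% / 3% | 10.7% / 5.8% | 0.314 | 0.406 (1.30) | 0.319 (1.02) |

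**A steeper assumption.** In a log-scale PASI model, patients below PASI 75 left with probability 10%, 25% or 50% per visit. Observed-case bias was −9%, −20% and −35% at 1.3%/1.8%, 2.9%/4.1% and 4.9%/6.9% drop-out; repeated-measures bias was −1% to −3%. The size therefore depends heavily on who leaves. No calculation was run for the patient-reported outcomes or for Groups 3 and 4.

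**The case against.** - **Part of this is already covered.** SAP 2.2.3 imputes serial change in PASI by dosing group and outputs estimated means, so for Groups 1 and 2 the plan is not purely observed-case. This stands. However, the imputed values feed only the PASI 90 logistic regression: no between-arm difference in mean PASI is produced, and the patient-reported outcomes are not covered.
- **Early leavers are not simply lost.** Their earlier values and EOT2 value are used at the visits where they fall. This stands; only later visits lose them.
- **The direction is not fixed.** A reader might infer that the 6-weekly versus 4-weekly difference is understated as a matter of fact, perhaps by a fifth or a third. The documents do not support that. They give no drop-out by arm or reason, and no Treatment Period 2 rule withdraws patients for losing PASI 90 or PASI 75. Factors above run from 0.35 to 1.43.
- **The bias is small in points.** With equal rules, the tabulated simulation gives 0.005 to 0.037 PASI points on a 0–72 scale. In the steeper model's middle case (bias about 0.10, SD 0.13–0.18), observed-case root-mean-square error is about 0.16–0.21, against an SD of 0.18–0.19 for the repeated-measures estimate. So there is no clear gain in total error. The gain is in removing a systematic error.
- **The MMRM result is partly built in.** Leaving depended on observed scores, so missing-at-random held by construction. This stands and is why the fix includes a sensitivity analysis.
- **These endpoints decide nothing confirmatory.** SAP 1.8.6 rests non-inferiority on the odds ratio interval alone, with drop-outs counted as non-responders. A reader might infer that the non-inferiority claim is compromised; it is not.

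**Conclusion.** The point holds as a modest weakness of the secondary analyses. Late-visit comparisons of mean PASI and the patient-reported outcomes are observed-case, while the SAP itself expects missingness related to outcome. Under that expectation, with the same drop-out rule in both arms and 6-weekly dosing somewhat worse, the late-visit difference is probably understated.

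The working size is roughly 2 to 13% at about 3 to 9% drop-out: 2%, 6% and 11% in the tabulated simulation, and 6 to 13% in the two-class cases where at most 20% of response losers leave. Larger figures arise if drop-out is concentrated in patients who have worsened most (20% at 5.5%/7.6% in the two-class table, or the steeper model) or if 6-weekly patients leave more readily. The sign reverses if 4-weekly patients do. All drop-out inputs are assumed, so neither size nor direction can be settled from the documents.

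Groups 3 and 4 share the weakness. The primary and key secondary conclusions are unaffected.

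**What to change.** In SAP 1.8.7 and 2.1.2, replace the separate ANCOVAs with one MMRM per endpoint and analysis set:

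- Use all scheduled Treatment Period 2 visits: Weeks 28 to 52 for PASI; Weeks 36, 48 and 52 for the patient-reported outcomes.
- Include dosing group, visit, dosing group by visit, country, body weight stratum and baseline value by visit.
- Specify unstructured covariance and name a fallback structure for non-convergence.
- Report the least-squares mean difference with 95% CI at each visit, and plot the PASI course from the model means.
- Keep observed-case summaries as descriptive tables.
- State that an early EOT2 value is analysed in the window of its study day and is not carried to Week 52.
- Add a sensitivity analysis assigning unfavourable values after drop-out for lack of efficacy.

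The cost is SAP wording and programming, with no new data. The model relies on missing-at-random given the observed scores, which the sensitivity analysis probes. Late-visit intervals may be somewhat wider: the SD of the Week 52 PASI difference in the steeper model was 0.18–0.19, against 0.13–0.18 for observed cases. With only three Treatment Period 2 visits, the patient-reported outcomes have less to gain than PASI.

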#### Overview of analysis methods for efficacy variables Table 1-7

Variable(s)	Summary statistics for binary/ categorical data	Risk Difference	Logistic regression	Summary statistics for continuous data	Analysis of Co- variance	Time to event data analysis
PASI 90 response at Week 52 for patients with PASI 90 response at Week 24	Х	Х	Х			
PASI 90 response at Week 52 for patients with PASI 75 response but without PASI 90 response at Week 24	X	Х	Х			
PASI 50/75/90/100 response from Week 28 to Week 52 (or Week 60)	X	X				
IGA mod 2011 0 or 1 response from Week 28 to Week 52 (or Week 60)	Х	Х				
Time course of PASI from Week 24 to Week 52 and change of PASI compared to baseline				X	Х	
Time course of DLQI from Week 24 to Week 52 and change of DLQI compared to baseline				Х	Х	
Time course of DLQI 0 or 1 from Week 24 to Week 52	Х	Х				
Time course of EQ-5D-5L from Week 24 to Week 52 and change of EQ-5D-5L compared to baseline	Х			X	Х	
Time course of WPAI-PSO from Week 24 to Week 52 and change of WPAI-PSO compared to baseline				X	Х	
Time course of assessment of pain itching and scaling from Week 24 to Week 52 and change of this assessment compared to baseline				X	X	
PASI 50, 75, 90 and 100 response at Week 24	Х					
IGA mod 2011 0 or 1 response at Week 24	Х					
Time to PASI 90 response from Week 24 on for patients with PASI 75 response but without PASI 90 response at Week 24						X
Time to loss of PASI 75 response from Week 24 on for patients with PASI 75 response but without PASI 90 response at Week 24						Х
PK data and PASI response during course of the study						
Time to loss of PASI 90						Х

Variable(s)	Summary statistics for binary/ categorical	Risk Difference	Logistic regression	Summary statistics for continuous	Analysis of Co- variance	Time to event data analysis
	data			data		
response after Week 24 for patients with PASI 90 response at Week 24						
Time to loss of IGA mod 2011 0/1 response after Week 24						Х
Body Surface Area affected by plaque-type psoriasis at Week 52 and change from baseline				Х		
Time course of PASI from Baseline to Week 24 and change of PASI compared to baseline				Х		
PASI 50/75/90/100 response from Week 1 to Week 20	X					
IGA mod 2011 0 or 1 response from Week 1 to Week 20	X					
Time course of DLQI from Baseline to Week 24 and change of DLQI compared to baseline				Х		
Time course of EQ-5D-5L Baseline to Week 24 and change of EQ-5D-5L compared to baseline				X		

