#### Patients assessment of pain, itching and scaling

Self-administered, 11-point numeric rating scales (NRS, 0-10) are used to evaluate the patient's assessment of their current pain, itching and scaling. Respondents answer the following questions for the assessment of:

- Pain: Overall, how severe was your psoriasis-related pain over the past 24 hours?
- **Itching**: Overall, how severe was your psoriasis-related itch over the past 24 hours?
- Scaling: Overall, how severe was your psoriasis-related scaling over the past 24 hours?

Patients have to rate their pain, itching, and scaling from 0 to 10 (11-point scale), with the understanding that the 0 represents the absence or null end of the pain, itching, or scale intensity (i.e., no pain, itching or scaling) and the 10 represents the other extreme of pain, itching, or scaling intensity (i.e., pain, itching or scaling as bad as it could be). The number that the patient selects represents his or her intensity score in the respective category.

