# Work Productivity and Activity Impairment Questionnaire Psoriasis (WPAI-PSO)

The WPAI-PSO is a self-administered questionnaire comprising of six questions about effects of psoriasis on the patient's ability to work and perform regular activities based on their experiences in the previous 7 days. The questionnaire quantifies the number of hours that the respondent was unable to work and, using a 10-point scale, evaluates the extent to which the respondent's psoriasis affected their productivity while working. For respondents who are not in paid employment, the questionnaire evaluates the extent to which the respondent's psoriasis affects their ability to perform regular daily activities.

The WPAI-PSO consists of six questions:

- Q1 = currently employed
- Q2 = hours missed due to health problems
- Q3 = hours missed due to other reasons
- Q4 = hours actually worked
- Q5 =degree health affected productivity while working
- Q6 = degree health affected productivity in regular unpaid activities.

The recall period for the questions 2 to 6 is seven days. Four main outcomes can be generated from the WPAI-PSO and expressed in percentages:

- % Absenteeism: percent work time missed due to health for those who were currently employed (i.e., only patients with Q1=Yes)
- % Presenteism: percent impairment while working due to health for those who were currently employed and actually worked in the past seven days (i.e., only patients with O1=Yes)
- % Total work productivity impairment: percent overall work impairment due to health for those who were currently employed (i.e., only patients with Q1=Yes)
- % Total activity impairment: percent activity impairment due to health for all respondents

The percentage of impairment while working (presenteism) is calculated as Q5/10 x 100%. The percentage of work time missed (absenteeism) is calculated as Q2/(Q2 + Q4) x 100%. The percentage of total work productivity impairment (i.e., work productivity loss) is  $(Q2/(Q2 + Q4) + (1-Q2/(Q2+Q4)) \times (Q5/10)) \times 100\%$ . The percentage of total activity impairment is

calculated as Q6/10 x 100%. In case of missing items the respective outcomes where these items are utilized cannot be calculated.

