#### 1.8.8 **Exploratory analyses**

All exploratory efficacy analyses for Treatment Period 2 will be performed by dosing group in the FAS-P90R and the FAS-P75R, separately. Exploratory analyses for Treatment Period 1 will be performed in the SAF-TP1. Analyses for Week 60 (rebound and relapse) will be based on the FUS.

### PASI and IGA mod 2011 0 or 1 response in Treatment Period 1

Summary statistics will be provided for absolute PASI scores in Treatment Period 1 as well as for absolute and percent change from baseline by visit.

Contingency tables for PASI 50/75/90/100 and IGA mod 2001 0 or 1 response in Treatment Period 1 will be presented by visit starting with Week 1 and will include absolute and relative frequencies.

#### DLQI, EQ-5D, WPAI-PSO and assessment of pain, itching and scaling in Treatment Period 1

For the DLQI subscale and the DLQI total score, the EQ-5D VAS and the EQ-5D utility index, for each of the main outcomes of the WPAI-PSO and for the assessment of pain, itching and scaling, the absolute and percentage change from baseline to week 4, 12 and 24 will be derived. Summary statistics will be provided for absolute values as well as for the percentage change by visit.

For the single EQ-5D dimensions contingency tables will be provided for each visit where the scale was to be assessed. Changes from baseline to each visit will be displayed using the categories *improved*, *unchanged* and *worsened* in each dimension.

#### Time to event analyses for PASI and IGA mod 2011 0 or 1 during Treatment Period 2

Kaplan-Meier analyses, log-rank tests and Cox proportional Hazard models will be performed for all time to event analyses in Treatment Period 2 with respect to the respective dosing groups in the analysis set. Further specifications of the applied statistical methods are provided in Section 2.3.

The analysis of time to PASI 90 response and the analysis of time to loss of PASI 75 response will be conducted in the FAS-P75R set, the analysis of time to loss of PASI 90 response in the FAS-P90R. The time to loss of IGA mod 2011 0 or 1 response will be performed in both patient sets for patients with IGA mod 2011 0 or 1 response at Week 24.

#### Body Surface Area affected by plaque-type psoriasis at Week 52

The absolute and percentage change from baseline to Week 52 will be derived. Summary statistics will be provided for absolute values as well as for the percentage change by visit for the FAS-P90R and the FAS-P75R.

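### Read literally, the SAP summarises change in the patient-reported scores only as percentage change, which is undefined at a baseline of 0; separately, WPAI total work impairment loses its worst value when Q5 is blank

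*SAP*

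**What the plan says.** **Change in the patient-reported scores.** In SAP 1.8.7, for Treatment Period 2, the variables to be derived for DLQI, EQ-5D (VAS and utility index), the WPAI-PSO outcomes and the pain, itching and scaling ratings are "the absolute and percentage change from baseline to each visit during" that period. The next sentence sets out what is tabulated: "Summary statistics will be provided for absolute values as well as for the percentage change by visit and dosing group". SAP 1.8.8 repeats the pattern for Treatment Period 1: "Summary statistics will be provided for absolute values as well as for the percentage change by visit". The PASI paragraph in 1.8.7 is worded differently and names all three quantities: "Summary statistics will be provided for absolute PASI scores as well as for absolute and percent change from baseline by visit and treatment group".

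SAP 1.8.7 also plans ANCOVA models for these scores at Weeks 36, 48 and 52 with the baseline value as covariate, rates of DLQI 0 or 1 with risk differences, and improved/unchanged/worsened tables for the EQ-5D dimensions. SAP 1.8.3 says missing values of secondary endpoints are not replaced.

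**WPAI-PSO.** SAP 1.8.1.3 defines presenteeism (from Q5) for employed patients who did some work in the past seven days. Total work productivity impairment is defined for all employed patients, and its formula uses Q2, Q4 and Q5. The missing-item rule is: "In case of missing items the respective outcomes where these items are utilized cannot be calculated".

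**The concern.** Zero is a legitimate baseline on most of these scales. DLQI runs from 0 to 30 (Protocol 6.6.2.1). On the rating scales "the 0 represents the absence or null end of the pain, itching, or scale intensity". Each WPAI outcome is 0% when there is no impairment. Entry severity is set on PASI, IGA mod 2011 and BSA only (Protocol 4.1), so no minimum applies to any patient-reported score, and the SAP has no rule for a zero denominator. A patient who starts at 0 can only stay the same or worsen, so any worsening in that patient is invisible in a percentage-change table. At baselines of 1 or 2 a small shift becomes a very large percentage.

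The WPAI rule raises a different problem. An employed patient who did no work has no natural answer to Q5. If Q5 is blank, total work impairment is not calculated, even when the whole week was lost to psoriasis and the answer is already determined. The value lost is always the worst one on the scale.

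At stake is the secondary objective on how maintenance frequency affects patient-reported outcomes.

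**Working it through.** The plan gives no figure for this point, so the check applies its own definitions.

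**1. Percentage change.** Formula: 100 × (post − baseline) / baseline.

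| Baseline | Post | Absolute change | Percentage change |
|---|---|---|---|
| 0 | 4 | +4 | undefined (division by 0) |
| 1 | 3 | +2 | +200% |
| 8 | 2 | −6 | −75% |

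For these three constructed patients, mean absolute change is (4 + 2 − 6)/3 = 0.0. Mean percentage change is (200 − 75)/2 = +62.5%, from two patients. The example shows the mechanism only; it does not predict the trial's data.

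**2. Size of the loss.** The documents give no share of patients starting at 0, so the shares below are assumptions. Group sizes are the planned 570 (Groups 1 and 2, Protocol 9.7) and 105 (Groups 3 and 4, Protocol 9.7.1).

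| Assumed share at 0 | Of 570 | Of 105 |
|---|---|---|
| 10% | 57 | 10 or 11 |
| 20% | 114 | 21 |
| 40% | 228 | 42 |

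These patients leave the percentage-change rows of that score and nothing else, provided the ANCOVA response is not percentage change. SAP 1.8.7 names that response for PASI (the absolute score) but not for the patient-reported scores.

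**3. PASI as contrast.** Baseline PASI is at least 10 by Protocol 4.1, so percentage change is always defined there.

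**4. WPAI total work impairment.** With a = Q2/(Q2 + Q4), the SAP formula is (a + (1 − a) × Q5/10) × 100%.

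- Q2 = 20, Q4 = 20, Q5 = 5: a = 0.5, so 0.5 + 0.5 × 0.5 = 0.75, or 75%. An ordinary case; Q5 is needed.
- Q2 = 40, Q4 = 0: a = 40/40 = 1, so 1 + (1 − 1) × Q5/10 = 1, or 100%. Q5 values of 0, 5 and 10 all give 100%.
- Q2 = 40, Q4 = 0, Q5 blank: not calculated under the missing-item rule. Absenteeism for the same patient is 40/40 = 100% and is kept.
- Q2 = 0, Q4 = 0 (for example, all hours missed for other reasons): a = 0/0, so the outcome is not calculable.

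Where the total is missing at a post-baseline visit, ANCOVA cannot use that patient at that visit. Where it is missing at baseline, the covariate and every change from baseline are missing too.

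**The case against.** **The wording is ambiguous.** The phrase about absolute values follows directly on a sentence deriving absolute change and could be meant to cover it. Table 1-7 lists "Time course of DLQI from Week 24 to Week 52 and change of DLQI compared to baseline", with parallel rows for the other instruments, and does not confine change to percentages. This stands as far as it goes: percentage change as the only change summary is the literal reading, not a certain one. But the PASI sentence names absolute change expressly, and 1.8.8 repeats the same contrast, so the text needs settling.

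**The effect is contained.** A reader might infer that both ends of these scales drop out of the analysis. The documents do not support that. Patients starting at 0 remain in the visit-level scores, the DLQI 0 or 1 rates, the EQ-5D categories and, unless its response is percentage change, the ANCOVA. The top end is at risk for one of four WPAI outcomes and for no DLQI, EQ-5D or rating-scale score.

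**No obvious bias between groups.** Baseline is Visit 2, 24 weeks before randomisation, so leaving out patients at 0 does not in itself bias Group 1 against 2 or Group 3 against 4. That is correct; what is lost is coverage and readability. The median is also reported (SAP 2.1.1), which softens the instability of the mean but does not restore the undefined cases.

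**The WPAI loss is conditional.** A reader might infer that the SAP sets patients who missed all work to missing. It contains no such rule. The loss occurs only if Q5 is blank; the documents show no skip instruction, and the bracketed condition on presenteeism mentions Q1 alone. All of this stands. A blank Q5 is nevertheless what one would expect from someone who did no work. How often this happens is unknown, and may be seldom in Treatment Period 2, when every randomised patient has had a PASI 75 response at Week 24.

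**Conclusion.** Two small gaps hold. First, on the literal wording of SAP 1.8.7 and 1.8.8, the only change summary for the continuous patient-reported scores is one that is undefined at a valid baseline value and unstable close to it, with no rule for either case. Its size depends on the unknown share of patients starting at 0. Second, the WPAI missing-item rule discards a determinate 100% for total work impairment when Q2 > 0, Q4 = 0 and Q5 is blank; its frequency is also unknown.

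A reader might also suspect that EQ-5D index baselines at or below 0 would reverse the sign of a percentage change. That depends on value sets the documents do not reproduce, and it forms no part of this conclusion.

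The point is minor. Only the primary and key secondary hypotheses are in the testing hierarchy (SAP 1.8.6), and neither is touched.

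**What to change.** - **SAP 1.8.7 and 1.8.8:** add absolute change from baseline to the summary sentences for DLQI, EQ-5D, WPAI-PSO and the three rating scales, as the main change measure. Percentage change may stay, restricted to patients with a non-zero baseline and with that n shown; dropping it altogether is a preference, not a necessity.
- **SAP 1.8.7:** name the response variable of the ANCOVA for these scores, as is already done for PASI.
- **SAP 1.8.1.3:** set total work productivity impairment to 100% when Q1 = yes, Q2 > 0 and Q4 = 0, whether or not Q5 is answered. State that Q2 = Q4 = 0 remains not calculable.

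The cost is wording, one derivation rule and slightly more tabulation. Absolute change is already derived, no new data are needed, and no confirmatory test changes.
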